7.2 Tumor Response Assessments

Objective response will be evaluated based on RECIST criteria Version 1.1 and irRECIST using CT scan or MRI scan or PET-CT scan. For patients with multiple measurable lesions, up to 5 lesions in total and 2 lesions per organ should be identified.

For Arm D (radiation), radiated target lesions will be evaluated with a modified version of the international criteria proposed by the RECIST Committee, version 1.1.

The exact technique used for measurement of lesions (i.e., either CT or MRI or PET-CT scan) will be left to the discretion of the investigator, however, for each patient the same technique must be used throughout the study, assessed whenever possible by

the same individual. The CT/ MRI abdomen must include the pelvis. A PET/CT is allowed, but ultrasound and x-ray of thorax is not allowed.

In cases where there is suspicion of progression before the next scheduled assessment, an unscheduled tumor assessment should be performed. In case a detected increase in tumor size is below the resolution limit of the CT/ MRI scanner, it is accepted to continue with treatment until a second assessment at a later time point unequivocally confirms progressive disease. Partial response requires confirmation with a follow-up scan at least 4 weeks apart.

If the increase in tumor burden is $\geq 20\%$ relative to nadir, then in the absence of rapid clinical deterioration, confirmation by a repeat, consecutive assessment no less than 4 weeks from the date first documented is recommended. Patients will continue with study drug until confirmation scan is obtained.

The following are defined as non-target lesions: bone lesions, leptomeningeal disease, pleural/pericardial effusion, ascites, inflammatory breast disease, lymphangitis, cystic lesions and lesions not measurable by CT or MRI. All non-target lesions are described over time and need not be measured.

The first evaluation of disease status by imaging will be done after 2 cycles or 8 weeks (± 7 days) of treatment and every 2 cycles or 8 weeks (± 7 days) thereafter at the physician's discretion. After completion of 1 year of treatment, tumor assessments will be performed every 3 cycles or 12 weeks (± 7 days) during treatment, independent of cycle delays.

Patients will also be eligible for the study if their disease is evaluable outside irradiated field on CT/ MRI.

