9.1 Analysis Sets

1) Safety Analysis Set

The safety analysis set includes all enrolled patients who receive at least one dose of each study medication in the assigned treatment combination. Patients in Arms A and D must receive at least one dose of avelumab and utomilumab each. Patients in Arm B must receive at least one dose of avelumab and PF-04518600 (OX40) each. Patients in Arm C must receive at least one dose of avelumab, utomilumab, and PF-04518600 (OX40) each. Subjects who have not received at least one dose of each study medication in the assigned treatment combination will be replaced.

2) Full Analysis Set

The full analysis set includes all enrolled patients.

3) Per Protocol Analysis Set

All enrolled patients who are eligible, receive study treatment and who either experience DLT during the first 56 days (following Cycle 1 Day 1) of study treatment or complete the 56-day treatment without DLT will be included. Patients who are lost to follow-up due to reasons unrelated to treatment related AEs are not evaluable for DLT.

The per-protocol population will consist of all patients who are compliant with study assessments and who have no major protocol violations that would compromise the assessment of efficacy. Major violations will be determined independently of knowledge of response to therapy. This population will be used for primary inferences concerning efficacy, however, if there are major differences between the results in this population and those obtained in the treated population, this will be taken into consideration in the decision to continue to later phase studies, or in the design of

further studies.

4) Response Analysis Set

All enrolled patients who are eligible, receive study treatment, have baseline assessments and at least 1 on-study tumor assessment will be considered evaluable for response. Patients who are treated and removed from study prior to on-study tumor assessment because of disease progression will be considered evaluable for efficacy and counted as failures.

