9.4 General Statistical Considerations

Tabulations will be produced for appropriate demographic, baseline, efficacy and safety parameters. For categorical variables, summary tabulations of the number and percentage of subjects within each category (with a category for missing data) of the parameter will be presented, as well as two-sided 95% confidence intervals, unless otherwise stated. For continuous variables, the number of subjects, mean, median, standard deviation (SD), minimum, and maximum values will be presented. Time-to-event data will be summarized using Kaplan-Meier methodology using 25th, 50th

(median), and 75th percentiles with associated 2-sided 95% confidence intervals, as well as percentage of censored observations.

No imputation of missing efficacy data is planned. For time to event analyses, patients who have no efficacy evaluations for disease recurrence will be considered censored at time 0.

For adverse events (AEs), missing dates will not be imputed, however, if partial dates are available, they will be used to assess if the AE occurred during the treatment period. Missing severities of AEs will not be imputed and will be considered missing in any tabulations of AE severity. If an AE is missing a response to the question regarding relationship to treatment, the event will be considered to be related.

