9.5 Efficacy Analysis

The treated population will consist of all patients who receive at least one dose of each study medication and have post-baseline efficacy follow-up information. This population will be used for primary analyses of efficacy.

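### A treated patient who never has an on-study scan counts as a response failure only if removed for progression; the others leave the denominator, so the response rate can only shift upward

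*Combined protocol and SAP*

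**What the plan says.** Section 9.1 defines the Response Analysis Set as eligible enrolled patients who "receive study treatment, have baseline assessments and at least 1 on-study tumor assessment will be considered evaluable for response". It makes one exception for patients without a scan: those "removed from study prior to on-study tumor assessment because of disease progression will be considered evaluable for efficacy and counted as failures". No other reason for a missing scan has a scoring rule.

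Section 7.2 sets the time of the first scan: "The first evaluation of disease status by imaging will be done after 2 cycles or 8 weeks", with a window of 7 days either way. Section 6.5 lists ways of leaving treatment other than progression, among them non-compliance, withdrawn consent, intercurrent illness, adverse events and investigator discretion. It lists death as a reason for leaving follow-up. Section 9.4 states: "No imputation of missing efficacy data is planned".

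Two other populations are also given a primary efficacy role. Section 9.5 defines a treated population of patients with "at least one dose of each study medication and have post-baseline efficacy follow-up information", and says: "This population will be used for primary analyses of efficacy". Section 9.1 says of the per-protocol population, which requires compliance with study assessments: "This population will be used for primary inferences concerning efficacy". The full analysis set holds every enrolled patient, but no efficacy analysis is assigned to it.

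**The concern.** A response can be documented only from an on-study assessment. A patient who leaves before any such assessment is therefore known not to be a documented responder. The plan uses that knowledge when the reason is progression and discards it otherwise. Removing known non-responders from the denominator, while leaving the numerator alone, pushes the estimate in one direction.

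Response rate is a secondary objective (Section 2.1.2), reported for each cohort with a 95% confidence interval (9.2). Preliminary efficacy contributes to the choice of the recommended phase 2 dose (3.5). Section 9.1 also says that major differences between the per-protocol and treated results will be weighed in the decision on later-phase studies. If both populations omit the same patients, comparing the two will not reveal the omission.

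**Working it through.** **Which populations keep an unscanned patient?**

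| Population | Section | Treated patient with no on-study scan, not removed for progression |
|---|---|---|
| Response Analysis Set | 9.1 | Out: needs at least one on-study assessment |
| Treated population | 9.5 | Can be out: needs post-baseline efficacy information and a dose of every drug in the combination |
| Per-protocol population | 9.1 | Can be out: needs compliance with assessments |
| Full analysis set | 9.1 | In, but no efficacy analysis uses it |

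The plan does not expressly assign the response rate to any one of these. The conclusion does not depend on which is used, because each of the first three can lose such patients.

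**Direction.** Let n be the number treated, x the number of responders and m the number dropped. The rate over all treated patients is x/n, and the rate as written is x/(n − m). Since x is unaffected by the dropping, x/(n − m) ≥ x/n, strictly so when x > 0 and m > 0. The inflation factor is n/(n − m).

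**Inputs.** n = 14 is the expansion cohort size (9.2). The documents give no target response rate, no expected number of responders and no expected number of unscanned patients. So x = 2 and m = 1 to 3 are assumptions for illustration, and there is no figure in the plan to reproduce for this point.

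**Method check.** The exact (Clopper-Pearson) limits are the 2.5% quantile of Beta(x, n − x + 1) and the 97.5% quantile of Beta(x + 1, n − x). For 3 of 20 they give 3.2% to 37.9%, which matches the interval in Section 1.2.1 for the gastric cancer cohort.

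**Fixed 14 treated, 2 responders, no replacement.**

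| Dropped (m) | Rate as written | Exact 95% CI | Factor 14/(14 − m) |
|---|---|---|---|
| 0 | 2/14 = 14.3% | 1.8% to 42.8% | 1.00 |
| 1 | 2/13 = 15.4% | 1.9% to 45.4% | 1.08 |
| 2 | 2/12 = 16.7% | 2.1% to 48.4% | 1.17 |
| 3 | 2/11 = 18.2% | 2.3% to 51.8% | 1.27 |

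Both confidence limits move up with the estimate.

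**Dropped patients replaced to restore 14.** The reported rate is then 2/14 = 14.3%, and the rate over all treated patients is lower.

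| Replaced | All treated | Factor |
|---|---|---|
| 1 | 2/15 = 13.3% | 15/14 = 1.07 |
| 2 | 2/16 = 12.5% | 16/14 = 1.14 |
| 3 | 2/17 = 11.8% | 17/14 = 1.21 |

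Which table applies is unclear. Section 3.3 replaces expansion patients who leave within 6 cycles for reasons unrelated to toxicity or progression, whereas Section 6.5 says patients withdrawn outside the DLT period are not replaced. Table 12 shows that totals of this size occur: Arm B treated 16 and Arm C treated 17 against 14 planned, after 2 and 3 replacements. The reasons are not given, so this does not show that those patients were unscanned.

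**The case against.** The strongest reply is that few patients will be affected. The Synopsis and Section 6.2 continue disease evaluations after a stop for any reason other than progression, death or withdrawn consent. Section 6.4 schedules follow-up scans, and the Synopsis adds a scan at end of treatment or withdrawal if none was done in the previous 8 weeks. A reader might infer that everyone who stops early for toxicity leaves the denominator, but the documents do not support that: a toxicity stop should ordinarily still lead to a scan. A smaller gap stands. A recent baseline scan could be taken to waive the end-of-treatment scan, follow-up scans cease at new anticancer therapy, and the plan does not say whether an off-treatment scan counts as on-study. Some early deaths may also be recorded as progression and so counted as failures.

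Second, Section 9.4 includes a category for missing data in categorical tabulations, and the Synopsis calls every patient with at least one dose eligible for analysis. The first could make unscanned patients visible if a broad population is tabulated. Neither makes them non-responders.

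Third, the endpoint is secondary and descriptive, with no threshold or test, and the shift is small beside the sampling error. This is correct and limits the weight of the point. The interval, however, describes random error and does not correct a one-directional shift.

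**Conclusion.** The point stands as a gap in the definition of the response denominator. The direction is certain whenever there is at least one responder and at least one treated patient who never has a scan for a reason other than progression. The size is not known, because the documents give no such count. In the illustration the increase is 1.1 to 3.9 percentage points without replacement (15.4 − 14.3 to 18.2 − 14.3), against an interval about 41 points wide (42.8 − 1.8).

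Three stronger readings are not supported:

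- **A distorted comparison between arms.** Section 9.2 estimates rates separately for each cohort and plans no between-arm efficacy comparison.
- **A bias in the trial's main result.** The primary endpoints are safety and CD8 biomarkers (2.2.1).
- **An expected share of dropped patients derived from the survival data in Section 1.2.1.** Those data come from an avelumab NSCLC cohort. This trial requires ECOG 0 to 1 and a life expectancy of at least 12 weeks (4.1), and the share of early deaths recorded as progression is unknown.

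**What to change.** In Sections 9.1 and 9.5, name one population for the response rate and for clinical response: all eligible patients who receive any study treatment, including those later replaced. State that a patient without an evaluable on-study tumor assessment, for any reason, counts as a non-responder. Report the scan-evaluable, treated (9.5) and per-protocol rates as sensitivity analyses, with the number of unscanned patients and the reasons.

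Rewriting the Response Analysis Set alone would not be enough, because the two populations called primary would keep the same exclusion. Their competing roles in 9.1 and 9.5 need to be reconciled in the same amendment. Sections 3.3 and 6.5 should also be brought into agreement on replacement, so that the number treated is well defined.

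The cost is a short text change in two sections plus the alignment of the replacement wording. No new data or visits are needed. The reported rate becomes slightly less favourable.

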9.2 Statistical Methods and Properties

As of Amendment Version 09, this study will be conducted in 4 arms. Arms A, B, and C will each enroll an MTD expansion cohort. Arm D will have a dose de-escalation and MTD.

In Arm D, standard 3 +3 dose de-escalation and MTD will be applied for dose level 1 and -1 with standard MTD and DLTs rule. We will use CTCAE criteria to capture adverse events related to the study drugs. If cohort 1 is not tolerable, there will be de-escalation to cohort -1.

Each study treatment arm will have an MTD expansion cohort of up to 14 patients each. The expansion cohort for each arm will be stopped early if the aggregate DLT rate $> 33\%$ for that particular arm. The aggregate DLT rate for each arm will include patients that were treated at the same dose level in the dose escalation or de-escalation phase. If the trial does not stop early, we will estimate the disease control rate and the response rate separately for each cohort with appropriate 95% confidence intervals. We will also estimate the progression free survival (PFS) and overall survival (OS) distributions using the Kaplan-Meier product limit method and report summary measures such as the median value and probabilities at selected times (again with appropriate 95% confidence intervals).

9.3 Sample Size Determination

During the course of the study, two to three dose levels were to be examined in each combination arm during the dose escalation/de-escalation with a standard “3+3” design, and a total of 3-6 patients will be enrolled per dose level. After each escalation or MTD determination by Pfizer, there will be an MTD expansion cohort of up to 14 patients each.

Prior to Amendment Version 05, Arm C was designed to have an escalation and 4 patients were enrolled; however, Pfizer provided recommendations for the MTD and requested that the MTD expansion commence. As of Amendment Version 06, the avelumab dosing for Arms A-C was revised; therefore, a new cohort of 14 patients each are expected to be enrolled for the MTD expansions of Arms A-C. As of Amendment Version 07, the original Arm G escalation and expansion (N= 32 total patients) cohorts have been removed from the study due to inability to accrue patients. Prior to Amendment Version 06, there was a total of 31 patients treated in the MTD expansions on the previous avelumab dosing schedule (Arm A: 8; Arm B: 12; Arm C: 11).

As of Amendment Version 08, the dosing schedules for Arms D-F were revised; therefore, Arms D, E, and F were re-initiated with the new schedule. Prior to Amendment Version 08, there were 11 patients enrolled on Arms D-F (Arm D: 4; Arm E: 3; Arm D: 4).

As of Amendment Version 09, the dosing schedule for Arm D was revised; therefore, Arm D dose de-escalation was to be re-initiated with the new schedule (2 dose levels of up to 6 patients each, or up to 12 patients total). Arms E and F were discontinued. Prior to Amendment Version 09, there were 20 patients enrolled on Arms D-F (Arm D prior to Amendment Version 08: 4 and Arm D on Version 08: 3; Arm E prior to Amendment Version 08: 3 and Arm E on Version 08: 3; and Arm F prior to Amendment Version 08: 4 and Arm F on Version 08: 3).

Thus, the planned maximum number of patients for the dose escalation/ de-escalation phase is 36 patients as indicated in Table 12. The planned maximum number of patients for the MTD expansion phase is 92 as indicated in Table 12. Therefore, the planned total maximum accrual in this study will be 128 patients (Escalation 36 + MTD

Expansions 92). Due to screen failures and replacement of inevaluable patients, up to 250 patients may be consented to this trial.

For the objective of describing the toxicity profile, descriptive statistics will be provided on the grade and type of toxicity by dose level. Clinical efficacy will be measured by objective tumor response per RECIST criteria. The clinical response is defined as a CR or PR or at least 6 months SD. A 95% confidence interval of response rate will be estimated based on a binomial distribution.

Table 12: Total Planned Accrual for Each Treatment Arm

Treatment Arm	Dose Escalation	MTD Expansion	Total Enrollment
Arm A: Avelumab + Utomilumab (4-1BB)	NA (Escalation at Pfizer)	N=8 (Prior to Amendment Version 06)	24
		N=16 (As of Amendment Version 06)	
Arm B: Avelumab + PF-04518600 (OX40)	NA (Escalation at Pfizer)	N=12 (Prior to Amendment Version 06)	28
		N=14 (As of Amendment Version 06) *Treated 16 after replacing 2 patients with IND Office Approval	
Arm C: Avelumab + Utomilumab (4-1BB) + PF-04518600 (OX40)	N=4 NA (Escalation at Pfizer)	N=11 (Prior to Amendment Version 06)	32
		N=14 (As of Amendment Version 06) *Treated 17 after replacing 3 patients with IND Office Approval	
Arm D: Avelumab + Utomilumab (4-1BB) + XRT		N=4 (Prior to Amendment Version 08)	33
		N=3 (On Amendment 08)	

Treatment Arm	Dose Escalation	MTD Expansion	Total Enrollment
	N=12 (As of Amendment 09)		
Arm E: Avelumab + PF-04518600 (OX40) + XRT	N=3 (Prior to Amendment Version 08)	Closed per Amendment Version 09	6
	N=3 (On Amendment 08)		
Arm F: Avelumab + Utomilumab (4-1BB) + PF-04518600 (OX40) + XRT	N=4 (Prior to Amendment Version 08)	Closed per Amendment Version 09	7
	N=3 (On Amendment 08)		
Total	36	92	128

MDACC Investigational New Drug (IND) Office, Medical Affairs and Safety Group will review safety and efficacy data with Principal Investigator (and statistician if needed), at a predetermined interval as indicated next:

PHASE I

The first analysis will occur after the first 3 evaluable subjects per arm (Arm D), are treated for 56 days from Cycle 1 Day 1 and prior to advancing/changing dose levels; and every 3 evaluable subjects thereafter.

PHASE II

Efficacy/toxicity analysis will occur every 7 evaluable subjects per arm when treated for 6 months after the first study therapy dose. Assess toxicity at the end of the first 56 days following Cycle 1 Day 1, and response after 6 months of treatment. On every report submission, the information from previous reported patients will need to be updated for response.

A copy of the cohort summary should be placed in the Investigator's Regulatory Binder under "sponsor correspondence".

Evaluation of toxicity based on the duration of radiation therapy:

if after 7 patients, 3 or more have a duration of radiation therapy greater than 8 weeks then the treatment should be considered excessively toxic in this cohort.

This will allow for identification of toxicity causing a delay in radiation which will translate to worse outcomes. Let p = true probability of duration of radiation therapy being > 8 weeks. Let q = probability of seeing 3 or more patients with excessive radiation duration out of 7 patients. Table 13 is a table of p and q .

Table 13: Probability

p	q
0.2	3%
0.3	13%
0.4	29%
0.5	50%
0.6	71%
0.7	87%
0.8	97%

9.4 General Statistical Considerations

Tabulations will be produced for appropriate demographic, baseline, efficacy and safety parameters. For categorical variables, summary tabulations of the number and percentage of subjects within each category (with a category for missing data) of the parameter will be presented, as well as two-sided 95% confidence intervals, unless otherwise stated. For continuous variables, the number of subjects, mean, median, standard deviation (SD), minimum, and maximum values will be presented. Time-to-event data will be summarized using Kaplan-Meier methodology using 25th, 50th

(median), and 75th percentiles with associated 2-sided 95% confidence intervals, as well as percentage of censored observations.

No imputation of missing efficacy data is planned. For time to event analyses, patients who have no efficacy evaluations for disease recurrence will be considered censored at time 0.

For adverse events (AEs), missing dates will not be imputed, however, if partial dates are available, they will be used to assess if the AE occurred during the treatment period. Missing severities of AEs will not be imputed and will be considered missing in any tabulations of AE severity. If an AE is missing a response to the question regarding relationship to treatment, the event will be considered to be related.

9.4.1 Demographics and Baseline Characteristics

The demographic characteristics to be summarized will include gender, race, ethnicity (Hispanic origin), and age at time of consent. For gender, race, and Hispanic origin, the summary statistics will be the number and percentage of patients within each group or the total sample. The categories for race will be those recorded in the database. For age at time of consent, the mean, median, minimum, maximum, and standard deviation will be provided for each group and the total sample.

Baseline characteristics include: Performance Status; duration from initial diagnosis; response to previous therapy (Y/N).

9.5 Efficacy Analysis

The treated population will consist of all patients who receive at least one dose of each study medication and have post-baseline efficacy follow-up information. This population will be used for primary analyses of efficacy.

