15. For patients on the PF-04518600 (OX40) Arms (B and C) who have had prior exposure to anthracyclines, cardiac enzyme monitoring will be performed at screening, Day 1 of every cycle, and End of Treatment. Troponin T and N-terminal of the prohormone brain natriuretic peptide (NT-proBNP) will be evaluated prior to dosing. No need to repeat on Cycle 1 Day 1 (C1D1) if the screening assessment is performed within 2 days prior to that date. Assessments performed on Cycle 2 Day 1 and Day 1 of each subsequent cycle should be performed within 48 hours prior to dosing. Assessments should also be performed when clinically indicated.
16. For MTD Expansion Arms A-C, avelumab will be administered IV every 2 weeks starting on Cycle 1 Day 15 (and then Days 1 and 15 of Cycle 2 and beyond).
17. For Arm A, utomilumab (4-1BB) will be administered IV every 4 weeks starting on Cycle 1 Day 1 (Day 1 of every cycle).
18. For Arm B, PF-04518600 (OX40) will be administered IV every 2 weeks starting on Cycle 1 Day 1 (Days 1 and 15 of every cycle).
19. For Arm C, utomilumab (4-1BB) will be administered IV every 4 weeks starting on Cycle 1 Day 1 (Day 1 of every cycle). PF-04518600 (OX40) will be administered IV every 2 weeks starting on Cycle 1 Day 1 (Days 1 and 15 of every cycle).
20. CT, MRI, or PET-CT Scans will be performed at screening, then every 2 cycles or 8 weeks +/- 7 days for the first year of treatment. Thereafter tumor assessments will be performed every 3 cycles or 12 weeks +/- 7 days during treatment, independent of cycle delays.
21. Tumor markers (if applicable) will be collected at screening, then every 2 cycles or 8 weeks +/- 7 days for the first year of treatment. Thereafter tumor assessments will be performed every 3 cycles or 12 weeks +/- 7 days during treatment, independent of cycle delays.
22. For MTD Expansion Cohorts in Arms A-C, tumor tissue will be obtained pre- treatment (baseline), between Cycle 1 Day 12-15 (prior to study drug dosing), prior to Cycle 3 Day 1 study drug dosing, and at progression (if achieved stable disease \geq 6 months, partial response, or complete remission) provided there is technically biopsiable tumor, and it is safe for patient to undergo biopsy.

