15. For Arm D, radiation will be given to 1-3 metastatic lesions. Radiation as described in Section 3.2 will be given during the Radiation Lead-in (Days -5 to -1) or 3 consecutive business days (+/-3 days). Cycle 1 Day 1 treatment should be within 3 days of last dose of radiation.
16. For Arm D, avelumab will be administered IV every 2 weeks starting on Cycle 1 Day 15 (and then Days 1 and 15 of Cycle 2 and beyond).
17. For Arm D, utomilumab (4-1BB) will be administered IV every 4 weeks starting on Cycle 1 Day 1 (Day 1 of every cycle).
18. CT, MRI, or PET-CT Scans will be performed at screening, then every 2 cycles or 8 weeks +/- 7 days for the first year of treatment. Thereafter tumor assessments will be performed every 3 cycles or 12 weeks +/- 7 days during treatment, independent of cycle delays.

19. Tumor markers (if applicable) will be collected at screening, then every 2 cycles or 8 weeks +/- 7 days for the first year of treatment. Thereafter tumor assessments will be performed every 3 cycles or 12 weeks +/- 7 days during treatment, independent of cycle delays.
20. For De-Escalation and MTD Expansion Cohort in Arm D, tumor tissue will be obtained pre- treatment (baseline), prior to Cycle 3 Day 1 dosing, and at progression (if achieved stable disease \geq 6 months, partial response, or complete remission) provided there is technically biopsiable tumor, and it is safe for patient to undergo biopsy.
21. For De-Escalation and MTD Expansion Cohort in Arm D, blood samples will be collected at baseline (prior to radiation), prior to Cycle 1 Day 1 dosing, prior to Cycle 1 Day 15 dosing, prior to Cycle 2 Day 1 dosing, prior to Cycle 3 Day 1 dosing, and at the time of progression (if patient had an initial response of stable disease \geq 6 months, partial response, or complete remission). Cell free DNA from patient's blood samples will also be analyzed.
22. Archival tissue may not be utilized for the baseline sample time point.

GLOSSARY OF ABBREVIATIONS

β-HCG	Beta human chorionic gonadotropin
1L	First Line Treatment
2L	Second Line Treatment
3L	Third Line Treatment
ADR	Adverse Drug Reaction
AE	Adverse event
ALC	Absolute lymphocyte count
ALT (SGPT)	Alanine aminotransferase
ANC	Absolute neutrophil count
aPTT	Activated partial thromboplastin time
AST (SGOT)	Aspartate aminotransferase
AUC	Area under the curve
BP	Blood pressure
BSA	Body surface area
BUN	Blood urea nitrogen
CA	Competent Authority
CDDP	Cisplatin
CHF	Congestive heart failure
CI	Confidence interval

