2.2.2 Secondary and Exploratory Endpoints

- Objective response rate determined by radiographic disease assessments per RECIST v1.1 and irRECIST.
- Progression-free survival, defined as the time from Cycle 1 start date until the earliest date of disease progression, as determined by investigator assessment of objective radiographic disease assessments per RECIST v1.1 and irRECIST, or death due to any cause, if occurring sooner than progression.
- Duration of response determined by radiographic disease assessment, defined as the time from earliest date of disease response until the earliest date of disease progression per RECIST v1.1 and irRECIST, or death due to any cause, if occurring sooner than progression.
- Overall survival determined from the Cycle 1 start date until death due to any cause.
- Response data in irradiated and non-irradiated lesions.
- Evaluation of various immune biomarkers from tumor and blood biospecimens.

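### The treated population in 9.5 requires a first avelumab dose at Cycle 1 Day 15, but PFS and OS run from Cycle 1 Day 1: median OS is overstated by about two weeks and scan-based PFS hardly at all

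*Combined protocol and SAP*

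**What the plan says.** Section 9.5 defines the efficacy population: "The treated population will consist of all patients who receive at least one dose of each study medication and have post-baseline efficacy follow-up information". It continues: "This population will be used for primary analyses of efficacy".

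For the Arms A to C expansions, footnote 16 of the Schedule of Assessments says "avelumab will be administered IV every 2 weeks starting on Cycle 1 Day 15". Footnote 16 of the Arm D schedule agrees: "For Arm D, avelumab will be administered IV every 2 weeks starting on Cycle 1 Day 15". The agonist starts on Cycle 1 Day 1 in every arm.

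Section 2.2.2 starts both clocks at Cycle 1: "Progression-free survival, defined as the time from Cycle 1 start date until the earliest date of disease progression" and "Overall survival determined from the Cycle 1 start date until death due to any cause". It counts death from any cause as a PFS event.

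Other provisions bear on the point:
- 9.1 item 1 replaces any patient who has not had a dose of each assigned drug.
- 9.2 plans Kaplan-Meier estimates of PFS and OS without naming a set, a landmark or delayed entry.
- 9.4 censors at time 0 patients with no efficacy evaluation.
- 9.1 item 3 (per protocol) has two paragraphs. The first takes patients who "either experience DLT during the first 56 days (following Cycle 1 Day 1) of study treatment or complete the 56-day treatment without DLT". The second takes compliant patients without major violations, and the sentence on primary efficacy inference follows it.
- 9.1 item 4 (Response Analysis Set) keeps patients removed for progression before a scan and counts them as failures.
- The synopsis makes everyone with at least one dose eligible for analysis.

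**The concern.** Entry to the treated population depends on something that happens about 14 days after the clock starts. No member can have died before the first avelumab dose, yet those 14 days count as survival time. These are single-arm cohorts, so no control group shares the bias and cancels it.

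Replacement adds to the problem, because an early failure gives way to a patient who did reach Day 15. So does 9.4: a patient who dies before the week-8 scan could be censored at time 0, although 2.2.2 makes that death a PFS event. The response rate can rise as well if early deaths or toxicity withdrawals leave the denominator. In cohorts of up to 14, a few such patients matter: 3 responders are 21% of 14 but 18% of 17. Because 9.1, 9.5 and the synopsis differ and 9.2 names no set, the choice could also be made after the data are seen.

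**Working it through.** The plan gives no target, event count or power for PFS or OS, so there is no figure of its own to reproduce.

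**Inputs**
- Landmark L = 14 days from Cycle 1 Day 1 to Day 15 (12 to 16 with the visit window).
- Background medians for avelumab in NSCLC, section 1.2.1: OS 8.4 months, PFS 11.6 weeks; for the PD-L1-negative subgroup, OS 4.6 months. Using them here is an assumption.
- First scan at 8 weeks, then every 8 weeks (section 7.2).
- Exponential survival, 30.4375 days per month (assumptions).

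**1. OS under the Day 15 condition.** With S(t) = 0.5^(t/m), the median among patients alive at L is m + L, and the share excluded is 1 − 0.5^(L/m).
- m = 8.4 months = 255.7 days: 255.7 + 14 = 269.7 days = 8.9 months (+5%). Excluded: 1 − 0.5^(14/255.7) = 3.7%, about 0.5 of 14 patients. Six-month OS goes from 61.0% to 63.3%.
- m = 4.6 months = 140.0 days: 140.0 + 14 = 154.0 days = 5.1 months (+10%). Excluded: 6.7%, about 0.9 of 14.
- With L from 12 to 16 days the shifts are +5% to +6% and +9% to +11%.

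This counts only deaths before Day 15. Patients who stop early but are still alive are dropped too; the documents give no figure for them.

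**2. PFS under the Day 15 condition, with progression found at scans.** The latent progression hazard is ln2/81.2 − ln2/255.7 = 0.00583 per day (11.6 weeks = 81.2 days). To be progression-free at 6 months (182.6 days), a patient must pass the scans at Days 56, 112 and 168 and be alive:
- All patients: exp(−0.00583 × 168) × 0.610 = 0.376 × 0.610 = 22.9%.
- Given alive at Day 15: 22.9% / 0.963 = 23.8%.

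A simulation of 1,000,000 patients gave the same percentages and a median PFS of 112 days in both groups, since progression is recorded on scan days. If 25% of progressions are seen clinically at once, 6-month PFS moves from 22.5% to 23.8%.

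**3. OS if the 56-day paragraph also governed efficacy.** Let q be the share of patients with a DLT, who are kept whatever their outcome. The retained share is D = q + (1 − q) × S(56), with S(56) = 0.859 at m = 255.7 days. The median solves S(t) = 0.5 × D.

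| q | D | Excluded | Median OS, days | Change |
|---|---|---|---|---|
| 0 | 0.859 | 14.1% | 311.7 (10.2 months) | +22% |
| 0.10 | 0.873 | 12.7% | 305.7 | +20% |
| 0.33 | 0.906 | 9.4% | 292.2 | +14% |

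The values of q are illustrative.

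**4. Scale against sampling error.** With 14 deaths, an approximate 95% interval for an exponential median is the estimate times exp(±1.96/√14), that is 0.59 to 1.69. A shift of 5% to 10% lies well inside it, but it is systematic and does not shrink if cohorts are pooled.

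**The case against.** The strongest reply is that the documents never assign PFS or OS to the treated population. Section 9.2 names no set, and 9.5.1 measures efficacy by tumor response. Broader sets also exist: a Full Analysis Set of all enrolled patients, and the synopsis rule of at least one dose. This is correct, and the link to PFS and OS is an inference. But 9.5 is the section that names a population for primary efficacy analyses, and nothing in the text makes one of the broader sets prevail for PFS or OS.

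A reader might infer several stronger things that the documents do not support:
- **That every efficacy set has the defect, so early failures always leave the response denominator.** The Response Analysis Set keeps early progressors as failures. It does not expressly keep early deaths or toxicity withdrawals before a scan, so only that part of the response concern stands.
- **That the per-protocol efficacy set requires 56 event-free days, raising median PFS by 69% (11.6 to 19.6 weeks).** The 56-day paragraph ends with a rule on DLT evaluability and reads as a DLT-evaluable set. The efficacy sentence follows the second definition, which has no such rule. The first paragraph also admits a patient with a DLT on any earlier day.
- **That the Day 15 rule raises median PFS by 17% (11.6 + 2 = 13.6 weeks).** That assumes progression is seen continuously. Unscheduled scans are allowed on suspicion, but the first planned scan is at 8 weeks.
- **That the Arm D clock should move to the first radiation fraction.** Nothing in the plan shows the Cycle 1 time zero to be defective there.

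Two further points stand. Eligibility requires ECOG 0 to 1 and a life expectancy of at least 12 weeks, so a constant hazard from Day 1 may overstate early deaths. And the 2 and 3 replacements that Table 12 records for Arms B and C have no stated reason, so they cannot be put down to missed avelumab.

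**Conclusion.** The point holds for the treated population in 9.5. Selecting on a Day 15 dose while counting from Cycle 1 Day 1 biases OS upward, by about two weeks on the median. The effect on scan-determined PFS is close to nil. Some inflation of response is possible, and 9.5 conflicts with the Response Analysis Set on who stays in the denominator. Whether the 56-day paragraph touches efficacy is ambiguous; if it does, OS inflation could reach about +14% to +22% at the 8.4-month median, so the ambiguity needs closing.

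The sizes rest on exponential survival, on medians borrowed from another avelumab trial, and on counting only deaths before Day 15. They apply to the current schedule; cohorts treated under earlier avelumab schedules are outside the calculation. Severity is moderate: the endpoints are secondary, descriptive and untested, and the cohorts are small.

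**What to change.** - In 9.2 and 9.5, estimate PFS, OS and response in all patients who received at least one dose of any study drug, as the synopsis allows, from Cycle 1 Day 1.
- Count deaths before the first scan as PFS and OS events and as non-responders, and state that the time-0 censoring in 9.4 does not apply to them. Replaced patients who had a dose stay in these analyses.
- Keep the each-drug subset as supportive only, either from a Day 15 landmark or with left truncation at the first avelumab dose.
- In 9.1 item 3, state that the 56-day paragraph defines the DLT-evaluable set only and is not used for PFS or OS. Align the Response Analysis Set with the new 9.5.
- Leave the Cycle 1 time zero unchanged, including for Arm D.

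The cost is SAP wording and slightly less favourable estimates. No extra patients or assessments are needed.
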